2.4.1 Risks of Blood Drawing

The participant may feel discomfort, dizzy, or light-headed during the blood draw. Where the needle enters the skin, bruising, swelling, or bleeding are possible. Every effort will be made to use existing indwelling lines for blood sampling.

The total participant blood volume drawn will not exceed the maximum blood volume allowed for the study period (see Section [6.7.5](#)).

2.4.2 Risk of Drug and Food Interactions

The participant must tell the study doctor or nurse about all the prescribed medical foods and drugs, herbal products, over-the-counter (OTC) drugs, vitamins, natural remedies, and alcohol they are taking before starting the study. In addition, participants should let the study staff know of any changes in medications or new products you start taking during the study.

2.4.3 Risk of Intravenous (IV) Infusion and Taking Blood from IV

The study drug is administered through an IV catheter which is a small, flexible hollow tube inserted into a vein in the arm. Inserting an IV requires a needle and can cause localized discomfort. The vein the catheter is inserted in may become inflamed with signs of redness and warmth at or near the IV insertion site. Inflammation in a vein due to a blood clot is also a potential risk. In some instances, the vein may develop a small rupture causing the drug to leak out of the vein. This is generally not dangerous, but can cause discomfort and bruising. There is a risk of infection; however, this is a small risk as aseptic technique will be used. Blood samples will be drawn from an IV. The potential risk related to this are: risk of infection into the bloodstream during blood draw procedure, pain or discomfort, inflammation of the vein known as phlebitis, and bruising at injection site.

2.4.4 Potential Risk of Loss of Confidentiality

Loss of confidentiality is a potential risk. Every effort will be made to protect the participant's confidential medical information, but this cannot be guaranteed.

2.4.5 Pregnancy Risks

Pregnancy is an exclusion for this study. Risks for pregnant women can be found in the methadone hydrochloride product label.³³

2.4.6 Unforeseen Risks

This research may present other risks to the participant that are not known or foreseeable at this time.

3 OBJECTIVES AND OUTCOME MEASURES

	Objective	Measures	Endpoints
Primary	Characterize the PK of methadone hydrochloride injection	Plasma concentrations	1. Clearance (CL) 2. Volume of distribution (Vz) 3. Half-life (t _{1/2}) 4. Area under the curve (AUC) 5. Maximum concentration (C _{max}) 6. Time to maximum concentration (T _{max}) 7. Minimum concentration (C _{min}) 8. Elimination rate constant (k _e)
Secondary	Characterize the PD effect of methadone hydrochloride injection	1. Dark-adapted pupillometry 2. Observed sedation 3. Thermal pain tolerance thresholds 4. Subjective self-assessment of methadone effects using visual analog scale (VAS)	Change in pupillometry, observed sedation, thermal pain tolerance thresholds, and VAS from pre-dose to each post-dose time point
Secondary	Characterize the tolerability of methadone hydrochloride injection	1. Adverse events (AEs) 2. Serious adverse events (SAEs) 3. Suspected Unexpected Serious Adverse Reactions (SUSARs) 4. Safety events of special interest (QTc)	For AEs, SAEs, SUSARs: Proportion of participants from baseline to the end of safety follow-up For SESI: Change in QTc from baseline to the end of safety follow-up
Exploratory	Characterize exposure-response relationships	Plasma concentrations and VAS	Correlation of plasma concentrations to VAS score at each post-dose VAS time point

4 STUDY DESIGN

4.1 Study Design

The trial aims to investigate the pharmacokinetics (PK), pharmacodynamics (PD), and safety of intravenous (IV) methadone hydrochloride in approximately 20 healthy adults. Eligible participants who have followed fasting and dietary requirements will be admitted to the Duke Early Phase Research Unit (DEPRU) for a single study-drug/methadone infusion and PK blood draws. The inpatient stay duration will be approximately 30 hours. Various assessments will be conducted from the inpatient visit to the final study visit, including: pupil diameter measurement, vital sign collection, Modified Observer's Assessment of Alertness and Sedation (MOAA/S), which measures sedation level evaluation, thermal pain tolerance assessment, subjective self-assessment using the Visual Analog Scale (VAS), Electrocardiogram (ECG) and safety evaluations. After discharge, participants will be asked to return to clinic at various time points over the subsequent 96 hours to provide blood samples for PK analysis and complete the various study procedures.

Study intervention: Single-dose trial of IV methadone hydrochloride

Study procedures: Pupillometry, vital sign collection, MOAA/S, thermal pain tolerance, ECG, VAS

Duration of participant participation: Up to 4 days after study enrollment, including up to 30 days for screening.

Biological specimen collection: Blood for PK, blood for pregnancy testing, urine for drug screening, breathalyzer, urine for pregnancy testing

Biological specimen retention plan: See Section [12](#)

4.2 Study Product or Intervention

4.2.1 Rationale for Dose Selection

The administered dose of 0.1 mg/kg methadone hydrochloride is the labeled dose for the treatment of pain in adults. The goal of this study is to better understand the PK of this labeled dose.

4.3 Duration of Participant Participation

The screening visit will occur 0-30 days prior to study start. From time of consent, participation may be up to 96 ± 8 hours after study drug administration, wherein the first 30 hours is an inpatient visit, including study drug administration and PK blood draws, followed by a 48 hour, and 72-hour follow-up. The final visit will occur at 96 hours.

4.4 Biological Specimen Collection

Blood samples will be collected from participants for PK analysis.

4.5 DOI-specific Testing

Blood samples obtained during the study will be analyzed for plasma concentrations of methadone and a methadone metabolite, EDDP, using a validated liquid chromatography with tandem mass spectrometry assay under Good Laboratory Practice conditions.

4.6 Events of Special Interest

4.6.1 Safety ESIs

Safety ESI includes QTc interval (ECG).

4.6.2 Efficacy ESIs

Efficacy ESIs include the following:

- miosis (dark-adapted pupillometry)
- ventilation (respiratory rate (RR), end-tidal expired CO₂)
- analgesia (thermal pain tolerance thresholds, VAS responses to methadone, self-reported assessments)

4.7 Study Definition of Enrollment

4.7.1 Study Definition of Enrollment into Active Study

Study enrollment is defined as a participant providing informed consent and receiving IV methadone.

4.8 Screen Failures

A participant will be considered a screen failure if he or she provided informed consent but did not receive IV methadone. This screen failure will be recorded on the disposition form in the EDC under "Did Participant Receive Study Drug?"

4.9 Study Definition of Completion

4.9.1 Participant Completion*

A participant will be considered complete if he or she received the single dose of IV methadone and was followed for safety through the last follow-up visit.

4.9.2 Study Completion

The study will be considered complete when all participants have completed the final visit and all required study and follow-up assessments.

*Participants not satisfying the above criteria for study completion will be reported as early terminators in the data system.

5 STUDY POPULATION

5.1 Selection of the Study Population/Sample Size

Approximately 20 evaluable healthy volunteers 18 to < 40 years old will be enrolled. Sex will be approximately equally distributed. Participants will be recruited from the greater Durham and Triangle community and a healthy volunteer registry in the DEPRU. Participants will be compensated.

5.2 Inclusion/Exclusion Criteria

Inclusion Criteria	
1. 18 to < 40 years of age at the time of enrollment2. Provides informed consent
Exclusion Criteria	
1. History of cardiac dysfunction2. History of or current QTc prolongation, defined as > 470 ms in males and > 480 ms in females3. Known hypersensitivity to methadone hydrochloride or any other ingredient in the methadone hydrochloride injection4. Known acute bronchial asthma or hypercarbia (history of known PaCO₂ above 45 mm HG)5. Receipt of a serotonergic drug or bupropion within 7 days prior to study enrollment6. Receipt of benzodiazepines, muscle relaxants, or other opioids within 7 days prior to study enrollment7. Receipt of a moderate or strong CYP2B6 inhibitor or inducer – either prescription or non-prescription medications, herbals,³⁴ or foods known to be metabolized by or affecting CYP2B6 within 30 days prior to study enrollment
a) CYP2B6 inhibitors include clopidogrel, prasugrel, thioTEPA, ticlopidine, voriconazole, macrolide antibiotics, azole-antifungal agents, fluconazole, Alstonia boonei, Mangifera indica, and Picralima nitidab) CYP2B6 inducers include artemisinin antimalarials, barbiturates, carbamazepine, cyclophosphamide, efavirenz, lopinavir, methimazole, nelfinavir, phenobarbital, phenytoin, primidone, rifampicin/rifampin, ritonavir, abacavir, amprenavir, nevirapine, telaprevir8. Receipt of zidovudine, desipramine, or other drugs that may increase serum concentration when combined with methadone within 30 days prior to study enrollment9. Known or suspected gastrointestinal obstruction, including paralytic ileus10. Significant respiratory depression (respiratory rate less than 8 breaths/min or oxygen saturation (SpO₂) <95%)11. BMI ≥ 33 and BMI ≤ 1712. Known history of moderate-to-severe liver (Child Class B or C) or kidney disease (serum creatinine > 1.5)13. Known history of drug or alcohol addiction (prior or present addiction or treatment for addiction)14. Females who are pregnant or nursing

5.3 Participant Discontinuation/Withdrawal

5.3.1 Participant Decides to Withdraw Consent

A participant may voluntarily withdraw consent to participate in the study at any time. No additional study procedures or data will be collected after consent has been withdrawn; however, all data and specimens collected up to the point of consent withdrawal will be maintained. The participant will be marked as early terminated from the study. The reasons for withdrawal, or failure to provide a reason, must be documented by the investigator. The participant is not obligated to state the reason for withdrawal.

5.3.2 Participant Decides to Withdraw from Study Intervention

A participant may choose to withdraw from the study intervention during or after receiving methadone for any reason but continue to be followed for all study assessments. The reasons for withdrawal from study intervention, or failure to provide a reason, must be documented by the investigator. The participant is not obligated to state the reason for withdrawal.

5.3.3 Study Investigator/Sponsor Decides to Withdraw Participant

The Study Principal Investigator (PI) or IND sponsor (i.e., a study authority) may withdraw a participant without consent if the following occurs:

- The participant's condition changes or a safety event occurs while on study, and the study is no longer in his or her best interest;
- The participant is non-compliant with the study protocol; or
- The entire study is stopped by the FDA, the sponsor, or other applicable party.

A participant who is discontinued from methadone due to an AE, whether serious or non-serious, must be followed by the investigator until the AE is resolved or considered stable. The medical monitor (MM) or Study PI must be notified if the AE possibly relates to methadone overdose. The package insert should be consulted for details of any specific actions to be taken ([link to package insert](#)).²⁹

If any of the above occurs, the participant will be informed of the withdrawal, and the investigator will discuss other options.

5.3.4 Replacements

In cases of early withdrawal from study, study dosing, or procedures – defined as a participant who has had < 5 specimens obtained – either by the participant or study authority, a replacement participant may be enrolled.

6 STUDY PROCEDURES

6.1 Summary of Procedures

Table 3. Schedule of study procedures and assessments

	Screening/ Enrollment	Inpatient Visit	Follow Up Visits		Final Study Visit	Early Withdrawal Visit
PROCEDURE	Day -30 to 0	Day 0, Hour 0 - 30	Hour 48 ± 8	Hour 72 ± 8	Hour 96 ± 8	
Informed consent	X					
Confirm eligibility criteria	X					
Demographics	X					
Physical examination	X					
Medical history	X					
Concomitant medications	X	X	X	X	X	
Pregnancy test	X	X ¹				
COVID-19 test ²		X ²				
Blood collection ³	X	X ³	X	X	X	X
Drug and alcohol screen	X	X				
Electrocardiogram	X	X			X	
Pupillometry		X ⁵	X	X	X	
Vital signs ⁴	X	X ⁵	X	X	X	
Observed sedation, MOAA/S		X ⁵	X	X	X	
Thermal pain tolerance		X ⁵	X	X	X	
Subjective self-assessment, VAS		X ⁵	X	X	X	
Study drug administration		X				
Safety events		X	X	X	X	X

¹ Serum quantitative testing will occur at screening and urine qualitative (point of care) testing will occur at the start of the in-patient visit.

² Per DUHS policy, COVID-19 testing may occur if the participant presents with new onset symptoms of COVID-19 or has had COVID-19 exposure within the last ten days.

³ See Sections [6.7.2.](#)(labs at Screening/Enrollment) and [6.7.4](#) (PK at Day 0) for details regarding blood sample collection times.

⁴ Vital signs collected at enrollment: respiration rate (RR), heart rate (HR), blood pressure (BP), and oxygen saturation (SpO₂). Vital signs collected at 30,48,72 and 96 hours: RR, carbon dioxide (CO₂), HR, BP, and SpO₂. See Section [6.8.3](#) for details.

⁵ See [Table 5](#) for details regarding collection times.

6.2 Screening/Enrollment (Day -30 to 0)

The investigator will screen participants according to the eligibility criteria (Section 5.2). Screening must remain impartial (no selectivity) to prevent bias.

Potential candidates' eligibility must be confirmed, or re-confirmed, and documented in the source records by the Study PI (or designee), prior to the conduct of any study procedures. Potential candidates will be educated on the study procedures, benefits, and potential risks as part of the applicable informed consent. Following consent, the enrolled participant's demographic information will be recorded, and the participant will undergo the following:

- Physical examination, including capturing weight and height
- Vital signs (heart rate, blood pressure, respiratory rate and oxygen saturation)
- Medical history
- ECG to determine QTc
- Review of concomitant medications
- Blood collection for clinical laboratory assessments (Section 6.7.2)
- Serum quantitative pregnancy test
- Urine drug screen to test for illegal and prescription drugs
 - Methamphetamine
 - Morphine-a drug in the opiate class
 - Marijuana
 - Amphetamine
 - Barbiturates
 - Benzodiazepines
 - Cocaine
 - Phencyclidine
 - Methadone
 - Ecstasy/MDMA
- Breathalyzer

For alcohol and substance abuse, the study team will query the potential participant about past and current drug and alcohol use or treatment of use, then document said testimony, which will be validated by the urine drug screen and breathalyzer.

This visit will occur up to 30 days before the inpatient visit to allow adequate time for the return of clinical laboratory results.

Refer to MOP for details.

6.3 Inpatient Visit (Day 0, Hour 0 - 30)

The study day will consist of an approximately 30-hour stay for participants in the DEPRU for methadone administration, blood sampling, and PD assessments. Abstinence requirements are listed in Section [7.3](#). The following will occur at the inpatient visit:

- Rapid COVID-19 test will occur per the DUHS policy if the participant presents with new onset symptoms of COVID-19, or reports COVID exposure within the last ten days,
- Urine qualitative pregnancy test
- Review of concomitant medications
- Urine drug screen and breathalyzer
- Blood collection for PK analysis (see Section [6.7.4](#) for timing of blood draw)
- Electrocardiogram for QTc, prior to study drug administration and 30 hours after study drug administration
- Pupillometry, goggles for dark-adapted pupil diameter
- Vital signs, including RR, end-expired CO₂, HR, BP, and SpO₂
- Observed sedation, MOAA/S
- Thermal pain tolerance threshold
- Subjective self-assessment, VAS
- Methadone hydrochloride administration
- Safety event assessment

Participants will be free to move around and be given a standard meal 4 hours after completion of methadone hydrochloride administration. Thereafter, participants will have free access to food and water while in the DEPRU. After the inpatient visit, participants should be transported home by a person previously arranged by the participant.

6.4 Follow-Up (48 to 72 hours post-drug administration)

At approximately 48, and 72 ± 8 hours after methadone administration, participants will return to the DEPRU for the following procedures:

- Review of concomitant medications
- Blood collection for PK analysis
- Pupillometry, goggles for dark-adapted pupil diameter
- Vital signs, including RR, end-expired CO₂, HR, BP, and SpO₂
- Observed sedation, MOAA/S
- Thermal pain tolerance threshold
- Subjective self-assessment, VAS
- Safety event assessment

6.5 Final Study Visit (96 hours post-drug administration)

At approximately 96 ± 8 hours after methadone administration, the final study visit will be in-person at the DEPRU and include the following:

- Review of concomitant medications
- Blood collection for PK analysis
- Electrocardiogram for QTc
- Pupillometry, goggles for dark-adapted pupil diameter
- Vital signs, including RR, end-expired CO₂, HR, BP, and SpO₂
- Observed sedation, MOAA/S
- Thermal pain tolerance threshold
- Subjective self-assessment, VAS
- Safety event assessment

6.6 Early Study Withdrawal Visit

In the event the participant chooses to terminate the study early, an early study withdrawal visit will include the following:

- Blood collection for PK analysis

- Safety event assessment

6.7 Specimen Collection for Study-Specific Tests

Refer to MOP for details.

6.7.1 Urine Collection

Urine will be collected for all participants at the screening visit to assess for illegal drugs. Urine will be collected from females of child-bearing potential at the inpatient visit for pregnancy status.

6.7.2 Screening laboratory assessments

Blood will be collected at the screening visit for the following assessments: serum pregnancy test (for females of child-bearing potential and CMP (complete metabolic panel). Fasting is not required. The CMP will be used to assess for exclusion criteria for those for known history of moderate-to-severe liver (Child Class B or C) or kidney disease (serum creatinine > 1.5).

6.7.3 Pharmacokinetic Tests

Blood specimens for methadone PK will be collected per the schedule in **Table 4**.

6.7.4 PK Sampling Schedule

The total number of PK blood samples will be 18, 2 ml/sample, 36 ml (less than one-quarter cup). Blood will be centrifuged and plasma removed and stored at -70°C until shipment to a laboratory for analysis. The time of each sample collection should be recorded.

Table 4. Optimal PK sampling schedule relative to single dose of methadone

PK Time Point Sample Number	Elapsed Time After Dose (hh:mm)	
1	Baseline draw	
2	Start IV dose 0:00 + 0:01 ¹	methadone HCl 0.1 mg/kg bw IV push over 1 -2 minutes (including 3ml 0.9NS flush immediately following study medication administration)
3	0:05 ± 0:01	
4	0:10 ± 0:01	
5	0:15 ± 0:01	
6	0:30 ± 0:05	
7	1:00 ± 0:10	
8	1:30 ± 0:10	
9	2:00 ± 0:10	
10	4:00 ± 0:30 ²	
11	6:00 ± 0:30	
12	12:00 ± 0:30	
13	18:00 ± 0:30	
14	24:00 ± 0:30	

15	30:00 ± 1:00
16	48:00 ± 8:00
17	72:00 ± 8:00
18	96:00 ± 8:00

¹Immediately after starting IV dose

²Food can be served after the 4:00 sample collection.

6.7.5 Maximum Blood Volumes

The maximum volume of fresh/non-scavenged whole blood to be collected is approximately 47 mL (equivalent to 3.2 tablespoons). A maximum of 18 blood samples of 2 mLs each can be obtained for each PK sample. A total of 8 mLs will be collected for on-site laboratory test: HCG (3.5 mLs and CMP 4.5 mLs). This total volume also includes a small amount of additional blood (3 mL) that is discarded prior to collecting each PK sample.

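### Section 6.7.5 counts a 3 mL discard once in its 47 mL blood maximum, but its wording attaches the 3 mL to each of 18 PK samples, which would give 98 mL

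*Combined protocol and SAP*

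**What the plan says.** Section 6.7.5 (Maximum Blood Volumes) sets the limit: "The maximum volume of fresh/non-scavenged whole blood to be collected is approximately 47 mL", which it equates to 3.2 tablespoons. It then lists three components.

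- **PK blood:** "A maximum of 18 blood samples of 2 mLs each can be obtained for each PK sample". Section 6.7.4 gives the same count and volume more clearly: "The total number of PK blood samples will be 18, 2 ml/sample, 36 ml".
- **Laboratory blood:** "A total of 8 mLs will be collected for on-site laboratory test", made up of 3.5 mL for HCG and 4.5 mL for the metabolic panel. Section 6.7.2 limits the first of these tubes to some participants: "serum pregnancy test (for females of child-bearing potential".
- **Discard:** "This total volume also includes a small amount of additional blood (3 mL) that is discarded prior to collecting each PK sample".

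The risk section relies on this limit. Section 2.4.1 states: "The total participant blood volume drawn will not exceed the maximum blood volume allowed for the study period", and refers to Section 6.7.5 for the figure.

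**The concern.** The discard sentence does two things that do not fit together. It says the discard is already inside the stated maximum, and it attaches 3 mL to every PK sample. With 18 PK samples scheduled, a 3 mL discard at each would by itself exceed 47 mL.

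This is the protocol's stated limit on blood drawn, and Section 2.4.1 makes it a commitment to participants. If the per-sample wording is right, the limit is understated. If the limit is right, the discard wording is wrong. The two cases need different corrections, and the protocol text does not let a reader choose between them. The stake is participant protection and accurate disclosure. No effect on the PK parameters or their analysis is at issue.

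**Working it through.** **Inputs**

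- PK samples: 18 at 2 mL each (Sections 6.7.4 and 6.7.5)
- Laboratory blood: HCG 3.5 mL and metabolic panel 4.5 mL (Section 6.7.5)
- Discard: 3 mL (Section 6.7.5)
- Stated maximum: about 47 mL, or 3.2 tablespoons (Section 6.7.5)

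**Formula.** Total = (samples × volume per sample) + laboratory blood + (discard per draw × number of draws with a discard).

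**Reproducing the stated figure**

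- PK: 18 × 2 = 36 mL
- Laboratory: 3.5 + 4.5 = 8 mL
- One discard: 3 mL
- Total: 36 + 8 + 3 = 47 mL, an exact match

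The tablespoon figure agrees: 47 / 14.787 = 3.18, stated as 3.2. The discard was therefore counted once.

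**Reading the discard as written**

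- Discard: 18 × 3 = 54 mL
- Total: 36 + 8 + 54 = 98 mL
- Excess: 98 − 47 = 51 mL; ratio 98 / 47 = 2.09
- Without the HCG tube: 36 + 4.5 + 54 = 94.5 mL; ratio 2.01

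**Narrower per-draw readings.** The documents state none of these; they show whether any per-draw reading could fit.

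| Assumption | Total |
|---|---|
| Discard at the 17 samples after baseline | 36 + 8 + 51 = 95 mL |
| Discard at the 15 samples through hour 30 | 36 + 8 + 45 = 89 mL |
| No discard at baseline or at the three follow-up draws (14 discards) | 36 + 8 + 42 = 86 mL |
| Same 14 discards, no HCG tube | 36 + 4.5 + 42 = 82.5 mL |
| 3 mL is the gross draw, including the 2 mL sample | 18 × 3 + 8 = 62 mL |

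None comes to 47 mL.

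**How many 3 mL discards fit within 47 mL**

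- With the HCG tube: (47 − 44) / 3 = 1.0. Two discards give 50 mL.
- Without it: (47 − 40.5) / 3 = 2.17. Two give 46.5 mL and three give 49.5 mL.

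**When the limit would be passed.** At 5 mL per PK draw (2 mL sample plus 3 mL discard) after 8 mL at screening, the running total is 8 + 8 × 5 = 48 mL at PK sample 8, scheduled at 1:30 in Table 4. Ten samples then remain. Without the HCG tube it is 4.5 + 9 × 5 = 49.5 mL at sample 9 (2:00).

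**Reading the 3 mL as the study total.** 47 mL stands, and the discard averages 3 / 18 = 0.17 mL per draw.

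**The case against.** The best defence is that the sum is correct and only a phrase is loose. The volume in brackets can be read as the whole amount included in the total, with the following clause merely saying what that blood is. On that reading the section closes exactly. The sentence also calls the discard small, whereas 54 mL would exceed all the PK and laboratory blood together (44 mL). The same section misuses the per-sample phrase just before, where it literally allows 18 samples for every PK sample, so the phrase is weak support for a 98 mL total.

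This has force. It makes a wording error as plausible as a volume error, and it means an understated maximum has not been shown. It does not remove the conflict. The study-total reading implies about 0.17 mL per draw, which no section states and which fits poorly with a discard made before each sample. Sections 2.4.1 and 2.4.3 describe sampling through indwelling or IV lines, so a discard at repeated draws is plausible.

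Two further points limit the claim. Sections 6.7 and 6.9 refer specimen collection to the manual of procedures, which may settle what site staff do; confusion at the bedside is therefore not established. The consent form was not available for this review, so an error in it cannot be asserted. Neither point cures the protocol text, because Section 2.4.1 names Section 6.7.5 as the limit. Nor can the qualifier on the 47 mL figure absorb totals of 82.5 to 98 mL.

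**Conclusion.** The concern holds. Section 6.7.5 is wrong as written: its maximum counts 3 mL of discarded blood once, and its wording assigns 3 mL to each of 18 samples. The two figures that matter are 47 mL, if 3 mL is the study total, and 98 mL, if 3 mL is discarded at every PK draw. The difference is 51 mL, about 2.1-fold. The totals between these rest on assumptions about which draws need a discard, and the documents do not give that information.

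Which reading was intended cannot be determined from the documents. No harm is shown, since they give no other blood-volume limit that 98 mL would breach. The text should be corrected because following Table 4 with the discard as worded would break the commitment in Section 2.4.1.

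**What to change.** Replace the discard sentence in Section 6.7.5 with one that gives the discard volume per draw, the number of draws it applies to, and the resulting maximum, calculated as 36 + 8 + (discard per draw × number of draws with a discard).

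- If 3 mL is discarded before all 18 draws, the maximum becomes 98 mL, and the tablespoon equivalent becomes about 6.6 (98 / 14.787).
- If 3 mL is the total for the study, 47 mL stays and the per-sample wording must change.

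Section 2.4.1 refers to Section 6.7.5 and needs no figure of its own. If the consent form or the manual of procedures states a blood or discard volume, make it agree.

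The cost is one corrected sentence. Under the per-draw reading the stated blood burden also becomes less favourable, and any volume in the consent form would need the same correction.
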